Hypothesis A: Young adult dual users, particularly males, will report lower satisfaction and higher withdrawal scores with episodes of e-cigarette use, in comparison to episodes of combustible tobacco product.

Aim 2: To examine gender differences in e-cigarette use patterns among young adult dual users.

Aim 3: To examine gender differences in e-cigarette use patterns among young adult dual users.

Hypothesis B: Young men will be more likely smoke/vape for the rewarding effects of nicotine.

Hypothesis C: Young women will be more likely to smoke/vape in response to contextual reasons.

Exploratory Aim: To examine sex differences in within-subjects' changes in cotinine levels during the dual use periods.

STUDY 2

2. Research Plan:

- a. **Overview:** In this one-year pilot study of 32 non-treatment seeking young adult e-cig/combustible tobacco product dual users (15 males/15 females), we will use smartphone-based ecological momentary assessment (EMA) to gather real-time data of e-cigarette and combustible tobacco product behaviors during a 1-week cig/e-cigarette dual use period. Participants will be eligible if they self-report use of e-cigarettes at least one day during the past 7 days and use of at least one other combustible tobacco product at least one day during the past 7 days. Participants will respond to daily random prompts assessing in-the-moment use of e-cigs/combustible tobacco products and the **subjective factors** (ratings of satisfaction and withdrawal) and **contextual factors** (location, activity, social cues) associated with each episode of use. They will also complete daily electronic diaries to document e-cigarette use episodes/day, amount of e-liquid used, combustible tobacco products smoked/day, nicotine concentrations and flavors used during the day, and how satisfied they were with the e-cigarette experience during the study. They will also be queried about whether they changed product constituents (flavors, numbers of flavors, nicotine concentrations). We will also collect markers of carbon monoxide and nicotine exposure (CO, cotinine) throughout the study.

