Participant Training upon Study Enrollment: The RA will teach participants to use the smartphone-based EMA data collection tool and to follow CM procedures. Participants will be instructed to: (1) continue smoking combustible tobacco products ad libitum without changing their smoking frequency/pattern during the study; (2) provide and use their own combustible tobacco products and e-cigarette and liquid during the study. The subjects will be paid for the week of EMA participation and CM-reinforced CO monitor video submissions at the follow-up appointment.

EMA data collection tool: We will use the MetricWire Android and iOS mobile applications (“apps”) for EMA data collection.(64) Participants will submit responses to survey questions and upload multimedia via the app. With guidance from the Canadian and U.S. Governments, the app is designed in careful reference to Good Clinical Practice (GCP), including the FDA’s part 11 HIPAA regulatory compliance. The app generates random prompts with the ability to set minimal interval time between prompts. Participants will also be prompted to complete daily night-time diaries. **5.1. Quality Checks and Procedures:** Data will be stored on a HIPAA and 21 CFR Part 11 compliant servers and encrypted during transit. Study investigators will have access through an encrypted web-based application. Participant data is uploaded from the mobile app when it is connected to wireless. The RA will check the database daily to complete and correct data entry.

STUDY 2

Contingency management (CM) procedure: On days 1-7, the MetricWire app will randomly prompt participants twice daily (in am and pm) to record a video of them blowing into the CO monitor. They will text/email (via their phone) the video to the study phone/e-mail. To promote video documentation, participants will receive \$1 for each on-time, valid video submission; this will continue to increase by \$1 per valid video submission for each consecutive daily video submission up to a maximum of \$14/day on Day 7 per Table 1. There will be a reset contingency for lack of video submission; participant’s payments will be reset to the initial (\$2.00/day) amount. The total possible CM payment is \$56, and total possible compensation for study participation is \$150 (Table 1).

UPDATED Table 1: Study 2 Study Flow and Contingency Management Reinforcement Schedule

WEEK 1	Day 0	1	2	3	4	5	6	7	DAY 8-10	TOTALS

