Daily Momentary Assessments: Participants will be randomly prompted with the MetricWire app up to 3x daily to provide data on e-cigarette/combustible tobacco product use in the last 15 minutes, the type of e-cigarette/combustible tobacco product used (brand/type), subjective factors (withdrawal) and the contextual factors surrounding the episode. **Subjective factors** will include *Mood* and *Withdrawal*. To maintain brevity during the random prompts, We will use the Mood and Physical Symptoms Scale (MPSS) to measure severity of five withdrawal symptoms (depressed, irritable, restless, hungry and poor concentration) and urge to smoke (craving).(65) Total score ranges from 5 to 25 with a higher score indicating a higher severity of withdrawal symptoms, we will use the International Positive and Negative Affect Schedule Short Form's measures of negative affect.(69) Participants will rate on a 5 point scale their agreement with experiencing the following emotion: (upset, hostile, ashamed, nervous, afraid). **Contextual factors** will include questions about *Companionship* (“During this smoking/vaping episode, who were you around?”) (smoker, person who is vaping, non-smoker, alone)), *Location* (“Where were you?”) (home, work/school, vehicle, bar/restaurant/store, other)), and *Activity* (“What were you doing?”) (eating/drinking a non-alcoholic beverage, drinking alcohol, working/reading/studying, traveling, socializing, other)). Participants will have 30 minutes to respond to random prompts; otherwise data will be considered lost. Each random prompt will be date- and time-stamped and record whether the assessment was completed, missed, delayed, or disbanded. *This method aims to accrue a representative sample of occasions focused on the participants' immediate state.*

STUDY 2

Daily Electronic (e-) Diaries: Participants will fill in daily night-time e- diaries via the app to provide data on e-cigarette use (episodes of e-cigarette use/ day) and combustible tobacco product smoking (# combustible tobacco products smoked/day). They will provide a rating of satisfaction with the e-cigarette they used during the day, and overall satisfaction rating of using their e-cigarette (1-10 Likert scales). Participants will record pictures of the e-cigarette(s) used during that day via the MetricWire app and provide a description of features. *We have chosen daily night-time e-diaries to minimize participant burden.*

STUDY 2

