a. Justification of Sample Size: Estimation of sample size (n=32) is based on achieving a clinically meaningful precision in effect size estimates for the primary outcome of interest. With 30 subjects we will be able to construct a 95% CI for the mean change in e-cigarette episodes/day from week 1 to 2 of width up to 0.37 standard deviations away from the mean (Aim 1) and 95% CI for the slopes of the regression relationships in Aim 2 of half-widths up to approximately 0.67 of the corresponding slope values. The obtained interval estimates will be used to inform future larger definitive studies.

Analysis Plan: Aim 1 will determine how within-subject's ratings of subjective factors (withdrawal, satisfaction with tobacco products) change between episodes of e-cigarette use vs. episodes of other combustible tobacco product use (cigarettes, cigars, cigarillos and/or hookah)

During e-cigarette and combustible tobacco product use periods. We will evaluate the variability in levels of satisfaction and withdrawal scores during these periods. Correlations between repeated measures on an individual will be modeled with random subject effects. Aim 2 will evaluate gender differences in e-cigarette use patterns among young adult dual users mean changes in e-cigarette use between the dual use and exclusive e-cigarette use period that differ by sex. We will evaluate changes in contextual factors and will assess effect sizes and construct 95% CIs for change in e-cigarette use

12. Data Management:

Quantitative outcomes will be collected using paper forms which will be double entered into a secure database. Error checking and data validation will occur weekly and any problems will be queried and resolved immediately. [name] will create monthly data quality reports to check for completeness and accuracy of key variables, as well as rates of recruitment, retention, and follow-up. Baseline demographics and smoking behaviors will be summarized. Continuous data will be expressed as mean values with standard deviations and categorical data will be presented as counts with percentages.

SECTION VII: RECRUITMENT/CONSENT AND ASSENT PROCEDURES

1. Targeted Enrollment: Give the number of subjects:

- a. targeted for enrollment at Yale for this protocol_32
- b. If this is a multi-site study, give the total number of subjects targeted across all sites _____

2. Indicate recruitment methods below. Attach copies of any recruitment materials that will be used.

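### Time since last use of each product is neither collected nor modelled, so the Aim 1 withdrawal contrast is open to carry-over of unknown size and direction

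*Combined protocol and SAP*

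**What the plan says.** - **Contrast.** Aim 1 (section 11, Analysis Plan) asks how ratings of withdrawal and satisfaction "change between episodes of e-cigarette use vs. episodes of other combustible tobacco product use". Hypothesis A expects that dual users, males above all, "will report lower satisfaction and higher withdrawal scores with episodes of e-cigarette use, in comparison to episodes of combustible tobacco product".
- **Prompt.** Under Daily Momentary Assessments (section 2.g), participants are "randomly prompted with the MetricWire app up to 3x daily" and asked about e-cigarette or combustible "use in the last 15 minutes, the type of e-cigarette/combustible tobacco product used (brand/type), subjective factors (withdrawal") and context. No item on time since last use is listed, and no rule covers a window in which both products were used. On response time: "Participants will have 30 minutes to respond to random prompts; otherwise data will be considered lost". The text does not say whether the 15 minutes run back from the prompt or from the response.
- **Use between prompts.** Participant Training (section 2.d) tells participants to "continue smoking combustible tobacco products ad libitum without changing their smoking frequency/pattern during the study". They use their own products, with no separation between them.
- **Other records.** The nightly diary takes e-cigarette episodes per day and "combustible tobacco product smoking (# combustible tobacco products smoked/day"), without clock time or order. The heading of 2.g mentions event-based sampling, but the text describes only random prompts and the diary. Breath CO videos are prompted twice daily on their own schedule.
- **Model.** Section 11 handles repeated measures with random subject effects. It names no term for previous product, time since use, or CO.
- **Outcome.** Section 2.e defines the primary withdrawal outcome as a daily mean.

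**The concern.** Withdrawal at a prompt reflects all recent nicotine, not only the product used in the last 15 minutes. Someone who smoked 20 minutes ago and has just vaped is recorded as an e-cigarette episode, exactly like someone who has not smoked all day. The reverse happens at combustible episodes. A random subject effect removes stable differences between people. It does not remove what the same person used shortly before a given prompt.

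The pilot's product is effect sizes with 95% CIs to inform later studies (section 11), so an unseen distortion would pass into their design. Hypothesis A also singles out males. If the sexes space or order the two products differently, that sex comparison would mix product effect with carry-over; the documents do not say whether they do.

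**Working it through.** **1. The plan's own figure.** Section 11 gives a 95% CI extending up to 0.37 SD from the mean with 30 subjects. t(0.975, 29)/√30 = 2.045/5.477 = 0.373, so it reproduces. It concerns the change in e-cigarette episodes per day from week 1 to 2. The plan gives no figure for the Aim 1 withdrawal contrast.

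**2. How often could carry-over be present?** From the plan: a 15-minute (0.25 h) look-back and at most 3 prompts × 7 days = 21 per person. The windows cover at most 3 × 15 = 45 minutes a day, or 45/960 = 4.7% of an assumed 16 waking hours. Also assumed, because the documents are silent: r combustible uses per day at random times, and a carry-over period of w = 1 or 2 hours. The share of e-cigarette episodes with combustible use within w hours but before the window is

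1 − exp[−(r/16)(w − 0.25)].

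| r per day | w = 1 h | w = 2 h |
|---|---|---|
| 1 | 5% | 10% |
| 5 | 21% | 42% |
| 10 | 37% | 67% |
| 15 | 50% | 81% |

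For example, r = 10 and w = 2 gives 1 − exp(−1.094) = 67%. Eligibility needs only one use day in 7 for each product. One combustible use a week (r = 1/7) gives about 1.5% at 2 h and 0.7% at 1 h.

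**3. Which way would it push?** Let c be the fraction of the previous product's relief still present, and ρ the correlation between the product types of successive episodes. If reliefs add, the previous episode contributes c times the product difference times ρ to the contrast, so

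observed contrast / carry-over-free contrast = 1 + cρ.

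For c from 0.1 to 0.7:
- ρ = −0.5 (products alternate): 0.95 down to 0.65
- ρ = 0 (random order): 1.00
- ρ = +0.5 (same product clusters): 1.05 up to 1.35

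**4. Simulation.** Assumed: episodes at random over 16 hours, 1, 4 or 10 a day for both products together; combustible relief twice that of the e-cigarette; half-life of relief 0.5, 2 or 4 hours; windows with both products dropped. Ratios of observed to carry-over-free contrast:

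| Relief | ρ = −0.5 | ρ = 0 | ρ = +0.5 |
|---|---|---|---|
| Additive | 0.79–0.99 | 1.00–1.07 | 1.02–1.59 |
| Saturating | 0.35–0.99 | 0.46–1.00 | 0.63–1.02 |

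At 1 episode a day every ratio lies between 0.90 and 1.06.

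**5. What would a restricted analysis keep?** Assume 10 uses a day of each product. Prompts with e-cigarette use in the window: 1 − exp(−10/16 × 0.25) = 14%, so about 3 of 21. Those with no combustible use in the last 2 hours: exp(−10/16 × 2) = exp(−1.25) = 29% of these, or 3 × 0.29 ≈ 0.9 episodes per person.

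**The case against.** The strongest reply is that the study is observational and sets out to describe naturalistic dual use. On that reading recent smoking is part of a real e-cigarette episode, and adjusting for it answers another question. This stands in part: the unadjusted contrast is legitimate and should be kept. It does not dispose of the point, because Hypothesis A attributes the difference to the product, and the third exclusion criterion is justified by wanting to isolate e-cigarette effects from pharmacotherapy. Without timing data a reader cannot tell which question has been answered.

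Three stronger readings are tempting, and the documents support none of them.

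- *The contrast is pulled towards zero.* Combustible nicotine before an e-cigarette episode narrows the hypothesised gap, but e-cigarette nicotine before a combustible episode widens it. The net effect depends on product order and on how reliefs combine, and the documents give neither. The withdrawal total has a floor of 5, which makes saturation plausible but does not show it. If product choice depends on current withdrawal, the bias could take either sign.
- *At 10 uses a day the estimate falls to one third (2 h) or two thirds (1 h) of the truth.* This takes 1 − 0.67 and 1 − 0.37 as ratios. It needs carry-over to erase the difference completely in every affected e-cigarette episode and to do nothing at combustible episodes.
- *Nothing can be done afterwards.* Time-stamped prompts with product type, diary counts and CO readings would allow coarse, partial adjustment for combustible exposure. The plan does not use them so, and they do not give the time since last use.

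**Conclusion.** The gap is real: the prompt, the diary and the model together cannot separate the product just used from recent use of the other, so the Aim 1 withdrawal contrast is open to carry-over. Its size and direction are unknown. In the scenarios tried, the contrast ranged from 0.35 to 1.59 times its carry-over-free value, and from 0.90 to 1.06 times at one episode a day. Those ranges rest on assumed half-lives, use rates, ordering and relief shape. The exposure shares rest on randomly timed use over 16 hours and an assumed 1- or 2-hour carry-over. None of these inputs is in the documents, so the numbers show only that the issue can matter for frequent users and is minor for infrequent ones. The unknown direction is itself a reason to collect the timing, since that would show which case applies. The point concerns withdrawal only.

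**What to change.** 1. Add two tick-box items to every prompt: time since last e-cigarette use and time since last combustible use (for example under 15 minutes, 15–60 minutes, 1–2 hours, over 2 hours). State the moment from which time is counted.
2. Put prompts with both products in the last 15 minutes into a separate 'both' category, outside the product contrast.
3. Run the Aim 1 contrast on prompt-level withdrawal scores. A daily mean cannot be assigned to either product on a day of mixed use.
4. Report that contrast twice: unadjusted, as the naturalistic comparison, and adjusted in the mixed model for time since last use of the other product. The adjusted version remains observational.
5. Treat any analysis limited to episodes without the other product in the last 2 hours as descriptive only, since few episodes per person would remain.

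The cost is a few seconds per prompt, at up to three prompts a day, and one covariate. The change does not touch satisfaction, which is rated daily in the diary, and it does not resolve the daily-mean definition of the primary withdrawal outcome in section 2.e.

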Due to poor recruitment levels with our original study design, we are requesting a revision of the protocol to reflect updated study procedures. As of 9/28/17- we have enrolled one patient in the study who has completed all study procedures. The data for this 1 participant will be analyzed, but not included in the total n for STUDY 2. This participant has completed all study procedures and will not be informed directly that the study 1 has been modified to STUDY 2, as the modification was not due to concern of risk to subjects, rather that a sufficient number of subjects in our local community did not meet eligibility criteria..

Our revised protocol (named STUDY 2), instead of focusing on both naturalistic dual use behaviors and behaviors while switching to e-cigarettes, now is focusing only on the naturalistic behaviors of 32non-treatment seeking young adult e-cigarette/combustible tobacco product dual users. Combustible tobacco products include **cigarettes, cigars, cigarillos, hookah, roll your own cigarettes**).

In this one-year pilot study of 32 non-treatment seeking young adult e-cigarette/combustible tobacco product dual users (16 males/16 females), we will use smartphone-based ecological momentary assessment (EMA) to gather real-time data of e-cigarette and combustible tobacco product behaviors during a naturalistic 1-week combustible tobacco product/e-cigarette dual use period. (1) Participants will respond to daily random prompts assessing in-the-moment use of e-cigarettes/cigarettes and the subjective factors (ratings of satisfaction and withdrawal) and contextual factors (location, activity, social cues) associated with each episode of use. They will also complete daily electronic diaries to document e-cigarette use episodes/day, amount of e-liquid used, cigarettes smoked/day, nicotine concentrations and flavors used during the day, and how satisfied they were with the e-cigarette experience during the study. They will be queried about whether they changed product constituents (flavors, numbers of flavors, nicotine concentrations). We will also collect markers of carbon monoxide and nicotine exposure (CO, cotinine) throughout the study.

STUDY 2

Aim 1: To determine how within-subject's ratings of subjective factors (withdrawal, satisfaction with tobacco products) change between episodes of e-cigarette use vs. episodes of other combustible tobacco product use (cigarettes, cigars, cigarillos and/or hookah).

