Study visit *	Baseline study visit (\$15)		a						F/U visit (\$15) and payment for EMA	\$30
Remuneration for EMA		Participant completed smart-phone based Ecological Momentary Assessments								\$50
85% EMA completion incentive										\$14
CO breath test: On-time/valid sample, regardless of the CO value (split for am/pm payment)		\$2 (\$1/\$1)	\$4 (\$2/\$2)	\$6 (\$3/\$3)	\$8 (\$4/\$4)	\$10 (\$5/\$5)	\$12 (\$6/\$6)	\$14 (\$7/\$7)		\$56
*Study visit activities: a) Review EMA procedures via phone									TOTAL:	\$150

Length of Study Visits

Baseline: 1.5 hours

STUDY 2 Follow-Up (Day 8-10): Up to 30 minutes

e. **Primary Outcome:** The primary outcomes are daily mean withdrawal scores (measured 3x/day with the Mood and Physical Symptoms Scale) and satisfaction with e-cigarette (measured daily with a 1-10 Likert scale).(65)

STUDY 2

f. **Baseline assessments Demographics:** age, gender, race, ethnicity, and level of schooling completed. **Combustible Tobacco Product Smoking:** Structured Timeline Follow-Back (TLFB) interviews will document the # of combustible tobacco products smoked per day during the past 28 days.(66) **E-Cigarette Use:** Structured TLFB interviews will document the # of episodes of e-cigarette use per day during the past 28 days. We will also query participants about nicotine concentrations used, flavors used, and the mls of liquid used/day. We already have extensive experience with the collection of these measures from work with adolescent e-cigarette users in the Yale TCORS project. **Nicotine Dependence:** Fagerstrom Test of Nicotine Dependence-R, a 6-item scale to estimate the severity of dependence.(67) **Abstinence Self-Efficacy:** The Smoking Self Efficacy Questionnaire to measure self-efficacy.(68) **Preferred Product Features:** Participants will be asked to bring their preferred cigarette and e-cigarette to the baseline visit. We will record the brand/type of cigarette and e-cigarette (brand, nicotine concentration, flavor, battery voltage, tank/cartridge size, propylene glycol/vegetable glycerin ratio).

STUDY 2

g. **Time based and Event based sampling procedure (EMA):**

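### Aim 1 compares satisfaction between products, but the detailed procedures rate satisfaction for e-cigarettes only, and the overview sections say otherwise

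*Combined protocol and SAP*

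**What the plan says.** Aim 1 asks how withdrawal and satisfaction differ within a person between e-cigarette episodes and combustible episodes. Hypothesis A predicts that dual users "will report lower satisfaction and higher withdrawal scores with episodes of e-cigarette use, in comparison to episodes of combustible tobacco product". The Analysis Plan in item 11 repeats the aim with both ratings.

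The plan gives two accounts of what is collected.

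- **Overview texts.** The Study 2 overview that precedes the aims says the random prompts gather "subjective factors (ratings of satisfaction and withdrawal) and contextual factors (location, activity, social cues) associated with each episode of use". Item 2.a (Overview) again lists "ratings of satisfaction and withdrawal" as what the prompts collect.
- **Detailed texts.** In item 2.g, Daily Momentary Assessments, the prompts collect use in the last 15 minutes, "the type of e-cigarette/combustible tobacco product used (brand/type), subjective factors (withdrawal) and the contextual factors surrounding the episode". The text then names mood and withdrawal as the subjective factors, with a scale for each. Under Daily Electronic Diaries, "They will provide a rating of satisfaction with the e-cigarette they used during the day", plus a second, overall rating that also concerns the e-cigarette. The diary entry for combustibles is a count: "combustible tobacco product smoking (# combustible tobacco products smoked/day"). Item 2.e defines the primary outcome as "satisfaction with e-cigarette (measured daily with a 1-10 Likert scale").

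Item 2.g is headed "Time based and Event based sampling procedure (EMA"), but its text describes only random prompts and a nightly diary.

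**The concern.** A within-person comparison of satisfaction needs a rating for each product. The overview texts promise one but give no item or scale. The section that specifies the instruments leaves satisfaction out of the prompts and restricts the diary ratings to e-cigarettes. Whoever programs the app will most naturally work from the detailed section. In that case the satisfaction part of Hypothesis A has no combustible side, and item 11's promise of an effect size with a 95% CI for each aim cannot be met for it.

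There is a second, smaller issue. If the overview texts are followed instead, a prompt yields a satisfaction rating only when a use falls inside its window. Prompts with no use still inform the withdrawal model, but they add nothing to the satisfaction contrast. Eligibility admits people who used each product on only one day in the past seven, and the plan gives no expected number of captured episodes per product.

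**Working it through.** **The plan's own Aim 1 figure.** Item 11.a gives a precision of 0.37 SD with 30 subjects. This reproduces as t(0.975, 29)/√30 = 2.045/5.477 = 0.373. It refers to change in e-cigarette episodes per day, so it says nothing about the precision of a satisfaction contrast.

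**Ratings available under 2.e and 2.g as written, for 32 people over 7 days.**

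| Source | Maximum per person | Maximum for 32 | E-cigarette satisfaction | Combustible satisfaction |
|---|---|---|---|---|
| Random prompts | 3 × 7 = 21 | 672 | none | none |
| Nightly diary, per item | 7 | 224 | yes | none |

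The count of combustible satisfaction ratings is 0. No assumption about use rates enters.

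**If a satisfaction item is asked at prompts.** The windows cover at most 21 × 15 min = 5.25 h per person. That is about 5% of an assumed 16 × 7 = 112 waking hours. For r episodes a day of each product, each lasting d minutes:

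- Chance that a prompt catches a product: p = 1 − exp[−r(15 + d)/(60 × 16)].
- Expected participants with both products caught: 32 × [1 − (1 − p)^21]².
- Worked case, r = 1 and d = 0: p = 0.0155; 1 − (1 − p)^21 = 0.280; 32 × 0.280² = 2.5.

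**If a combustible item is added to the nightly diary.** The chance that a product is used on a given day is q = 1 − exp(−r). Participants with at least one rated day of each product number 32 × [1 − (1 − q)^7]². At r = 1 this is 32 × [1 − exp(−7)]² = 31.9.

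**Half-widths.** With n_e and n_c ratings per person, the information is the sum over people of n_e·n_c/(n_e + n_c), and the 95% half-width is 1.96/√information. With every diary day rated for both products this is 1.96/√(32 × 3.5) = 0.19. The other values are medians of simulated trials (3,000 for prompts, 400 for the diary).

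| Episodes/day of each | Both caught by prompts, d = 0 / 10 / 30 min | Prompt half-width, d = 0 / 10 min | Both rated in diary | Diary half-width |
|---|---|---|---|---|
| 1 | 2.5 / 5.7 / 12.6 | 1.75 / 1.07 | 31.9 | 0.24 |
| 2 | 7.4 / 14.2 / 23.7 | 0.92 / 0.62 | 32 | 0.20 |
| 5 | 20.8 / 28.0 / 31.5 | 0.46 / 0.34 | 32 | 0.19 |
| 10 | 29.6 / 31.7 / 32.0 | 0.30 / 0.23 | 32 | 0.19 |

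At one episode a week of each product, the diary gives 32 × [1 − exp(−1)]² = 12.8 participants and prompts give 0.1 to 0.6. If only 85% of prompts are answered, the d = 0 counts fall to 1.9, 5.8, 18.0 and 28.1.

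Prompt half-widths are in SDs of momentary ratings and diary half-widths in SDs of nightly ratings. The two columns measure different things and should not be read as a direct precision comparison.

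**The case against.** The strongest reply is that the overview texts do say satisfaction is rated for each episode. Item 2.g says only what the subjective factors will include, which need not be an exhaustive list, and the EMA form itself is not in the text available. This stands to the extent that the documents prove a contradiction. They do not prove that the ratings will be missing. The zero is conditional on 2.g being the complete item list.

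A second reply concerns the yield figures. Use rates, episode durations and waking hours are all assumed, and the counts run from 2.5 to 32.0 of 32. At five 10-minute episodes a day, 28.0 of 32 participants contribute, which is hardly a problem. That is right. The yield point is secondary and matters only for light users, whom eligibility does admit.

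Third, a nightly rating is recalled over the day, so it does not test an episode-level hypothesis as worded. The half-widths also assume the same product effect in everyone, although Hypothesis A itself expects men to differ. Both points stand. If the product effect varied between people with an SD equal to the within-person SD, the diary half-width at one episode a day would rise from 0.24 to about √(0.24² + (1.96/√32)²) = 0.42.

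Finally, this is a pilot sized for interval estimation, and its stated primary outcomes need no captured episode. That limits the weight of the point but does not supply the missing rating. The unmatched event-based wording in the 2.g heading is largely editorial, since the text gives a rationale for random sampling.

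**Conclusion.** The concern holds. The plan contradicts itself on whether satisfaction is rated at the prompts, and nowhere does it specify an item or scale for satisfaction with a combustible product. Followed as 2.e and 2.g are written, the study yields no combustible satisfaction ratings, and the satisfaction half of Aim 1 and Hypothesis A cannot be estimated. That conclusion rests on the text alone, read as a complete item list.

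The secondary conclusion is that a prompt item alone would be imprecise at low use rates. It depends on equal and independent use of the two products, 16 waking hours, all 21 prompts issued and answered, and a common product effect, and it largely disappears at high use rates. The withdrawal contrast is collected at the prompts, and the item 2.e primary outcomes are not affected.

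**What to change.** Reconcile the Study 2 overview and item 2.a with items 2.e and 2.g, and specify the satisfaction measure for both products:

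- Add one 1-10 satisfaction item to the existing random-prompt form, asked for each product reported in the last 15 minutes. This gives the episode-level contrast that Aim 1 describes.
- Add a matching 1-10 combustible satisfaction item to the nightly diary, shown when that day's combustible count is one or more. This gives a day-level contrast that does not depend on catching an episode.
- State in the Analysis Plan which of the two tests the satisfaction part of Hypothesis A, and label the other as supportive.

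The cost is one item at prompts that report use (two if both products were used), at most one item a night, and a few lines of analysis text. No extra prompts, visits, staff or participants are needed. The drawbacks are slightly longer forms, against the plan's stated aim of brevity, and a diary rating that relies on recall over the day. The change has to be made before data collection, because the missing ratings cannot be reconstructed later.
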